## 10.2 Testing Hierarchy

This is a single primary efficacy endpoint (PFS, Arm A vs Arm C) study. Survival data (a total of approximately 136 death events targeted across all three treatment arms) will not be mature at the PFS primary analysis time, thus OS analysis at the time of PFS primary analysis will be considered as an interim analysis. If statistical test is significant (one-sided P value  $\leq 0.1$ ) for the primary efficacy endpoint, then the fixed sequence testing procedure will be performed with a significance level of 0.1 (one-sided) for key secondary efficacy endpoints sequentially. If primary PFS (Arm A vs. Arm C) is not significant, then statistical significance will not be declared for any of the secondary efficacy endpoints.

Hierarchical ranking and alpha spending for primary and each secondary endpoint at the time of PFS primary analysis and OS primary analysis is presented in [Table 5](#).

**Table 5. Alpha-spending Boundary (One-sided p-value) for Each Ranked Endpoint**

Endpoint	Timing	
	PFS Primary Analysis (approximately 126 PFS events across all 3 arms)	OS Primary Analysis (approximately 136 deaths across all 3 arms)
PFS (A vs C)	0.1	NA
OS (A vs C)	0.0001 (administrative purpose)	0.1
PFS (B vs C)*	0.1	
OS (B vs C)	0.0001 (administrative purpose)	0.1
ORR (A vs C)*	0.1	
ORR (B vs C)*	0.1	

(A, B, and C correspond to the three treatment arms, respectively.)

\* Analysis sets for these three tests are the same as PFS (A vs C).

### 10.3 Definition of Efficacy Endpoints

**PFS (progression-free survival):** the number of days from the date of randomization to the date of earliest radiographic disease progression or death provided no radiographic disease progression occurred.

All events of disease progression before the initiation of anti-cancer post-treatment therapy will be included, regardless of whether the event occurred while the subject was still taking study drug or had previously discontinued study drug. However, if a disease progression event occurs immediately after a subject misses two or more consecutive disease progression assessments (e.g., 84 days = 12 weeks if previous tumor scan were prior to or on Week 24 Day 7 (Day 168), 105 days = 15 weeks if previous tumor scan were in between of Week 25 Day 1 and Week 30 Day 7 (Day 210), and 126 days = 18 weeks if previous tumor scan were on or after Week 31 Day 1), then this subject's data will be censored at the last disease progression assessment prior to the missing disease progression assessments, or at randomization if disease progression occurred at the first post-baseline disease assessment. All events of death before the initiation of anti-cancer post-treatment therapy will be included for subjects (whether had post-baseline tumor assessment or not) who had not experienced disease progression, regardless of whether the event occurred while the subject was still taking study drug or had previously discontinued study drug. Similar to disease progression, if a death event occurs immediately after a subject misses two or more consecutive disease progression assessments (length of gap is calculated the same way as disease progression), then this subject's data will be censored at the last tumor assessment before death, or at randomization provided subject did not have any post-baseline disease assessment.

If a subject did not have an event of disease progression nor has the subject died on or prior to the cutoff of PFS analysis, this subject's data will be censored at the date of his/her last disease assessment or randomization date provided subject did not have any post-baseline disease assessment.

**OS (overall survival):** the number of days from the date of randomization to the date of death. All events of death will be included.

If a subject did not die on or prior to the cutoff of OS analysis, this subject's data will be censored at the date of his/her last known alive date, which is defined as the last date of the last survival follow-up visit, the start date of the last AE, the start date or end date of the last dose of any study drugs, the last lab and vital sign collection date, or the last disease assessment date, whichever occurs the last.

**ORR (objective response rate):** the proportion of randomized subjects with objective response (confirmed) as assessed by the investigator using RECIST version 1.1. Response includes both CR (complete response) and PR (partial response). Confirmation is required to determine objective response. Confirmation rules are described as follows,

Confirmed CR: After the first tumor assessment showing CR, the CR will be considered confirmed if the very next tumor assessment also shows CR (with no other responses in between), and if the duration between the two CRs is greater than or equal to 28 days.

Confirmed PR: After first tumor assessment showing PR, the PR will be considered confirmed if a subsequent tumor assessment also shows CR/PR (irrespective of tumor assessment in between that show stable disease) and if the duration of the first PR and the next CR/PR is greater than or equal to 28 days.

All ITT subjects will be included in the ORR analysis. Subjects with no post-baseline confirmed response will be identified as non-responders. Data after the first appearance of PD, or the start date of any anti-cancer post-treatment therapy, whichever comes earlier, will not be included.

**DOR (duration of overall response):** the number of days from the date of the first confirmed response (CR or PR) to the earliest documentation of radiographic progressive disease or death. The inclusion and exclusion criteria for PD and death, as well as event censoring strategy, are the same as described in PFS endpoint.

If a subject is still responding on or prior to the cutoff of DOR analysis, then the subject's data will be censored at the date of the subject's last available disease assessment.

Subjects with no post-baseline confirmed response will not be included in the DOR analysis. Data after the first appearance of PD, or the start date of any anti-cancer post-treatment therapy, whichever comes earlier, will not be included.

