**Table 8. Study Activities in Phase 2 (Continued)**

- a. Screening visit must be performed within 28 days of Cycle 1 Day -2. If the screening visit is performed > 7 days prior to Day -2 the physical exam, laboratory tests (hematology and chemistry) and pregnancy test must be repeated on Cycle 1 Day -2. Tumor assessments must be performed within 21 Days of Cycle 1 Day -2.
- b. The informed consent must be signed and dated prior to the initiation of any screening or study specific procedure being performed.
- c. A subject's medical history will be reviewed at each visit. Any changes from baseline will be recorded on the adverse event eCRF.
- d. Physical exam does not need to be repeated at Cycle 1 Day -2 if screening physical exam was completed within 7 days of Cycle 1 Day -2. Physical exams during combination cycles must include assessment of hearing if required by the local SmPC for carboplatin. The Cycle 1 Day 8 physical exam may be symptom directed. Height will be assessed at Screening only.
- e. A serum pregnancy test must be performed at Screening, a urine pregnancy test on Cycle 1 Day -2 prior to dosing if > 7 days since obtaining the serum pregnancy test for women of childbearing potential. Pregnancy tests may be repeated at any time during the study at the discretion of the investigator.
- f. Hematology and Chemistry panels do not need to be repeated at Cycle 1 Day -2 if screening labs were completed within 7 days of Cycle 1 Day -2. A central laboratory will be used for the study; however, sites may use a certified local laboratory to collect a sample to dose the subject. If local labs are drawn the sample MUST be split and also sent to central lab.
- g. Only for subjects with known history of HBV or HCV without prior evidence of active disease-free status and if HBsAg/HCV RNA status within 3 months of the study entry is unknown.
- h. If clinical disease progression is suspected, progression must be confirmed radiographically per RECIST 1.1. Clinical disease progression will include, but will not be limited to worsening performance status due to progressive disease, requirement for non-palliative radiation therapy, alternative chemotherapy or surgery due to progressive disease. At the Final Visit, a clinical disease progression assessment is required only for subjects who discontinue the study for reasons other than progression (clinical or radiographic).

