## **10.0 Efficacy Analysis**

### **10.1 General considerations**

Unless otherwise noted, for all statistical analyses, statistical significance will be determined by a one-sided P value  $\leq 0.1$  (when rounded to two decimal places). Confidence intervals will be two-sided 80% for all descriptive statistics. The date of randomization is defined as the date that the IRT issued a subject number.

The efficacy analyses will be performed on Phase 2 ITT population and presented by treatment arm. All randomized subjects will be included unless otherwise specified. The dosing schedules for each of the three arms are listed in detail in Section 4.2.

After observing 95 PFS events (75% of 126), a model-based prediction was performed to estimate the approximate date of the 126th PFS events across all 3 arms. The prediction estimated Sep. 14th, 2018 as the date of 126 PFS events across the three arms. Unless otherwise specified, Sep. 14th, 2018 will be the cutoff date for all efficacy analyses.

For all efficacy endpoints except OS, if a subject's blind has prematurely broken by sites before cutoff date, the date of premature blind break will be set as the cutoff date for that subject.

If a subject starts any systemic anti-cancer therapy post-discontinuation of study therapy, then PFS and DOR will be censored at last non-missing tumor assessment prior to the initiation date of the new systemic anti-cancer therapy; similarly ORR/DOR will be based only on tumor assessment prior to the initiation of any new systemic anti-cancer therapy.

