## **10.8 Additional Efficacy Analysis**

The following additional efficacy analysis may be performed:

1. Modified PFS analysis for Arm A & Arm C to consider the initiation of any anti-cancer post-treatment therapy as an event.
2. Modified ORR analysis for Arm A & Arm C and DOR analysis for all 3 arms where both confirmed and unconfirmed responses are to be considered.

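### The day counts given for the missed-assessment censoring of PFS (84, 105, 126) are one-missed-scan gaps, although the rule is worded for two or more

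*SAP*

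**What the plan says.** SAP 10.3 gives the PFS rule in words and in days within one sentence. A progression is censored if it directly follows the missing of "two or more consecutive disease progression assessments (e.g., 84 days = 12 weeks if previous tumor scan" fell on or before Day 168). The next tier is "105 days = 15 weeks if previous tumor scan were in between of Week 25 Day 1 and Week 30 Day 7 (Day 210"), and the last is 126 days (18 weeks) for a previous scan from Week 31 Day 1 on. The subject is censored at the last assessment before the gap, "or at randomization if disease progression occurred at the first post-baseline disease assessment". For deaths, the "length of gap is calculated the same way as disease progression". For DOR, the treatment of progression and death, "as well as event censoring strategy, are the same as described in PFS endpoint".

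The Protocol (Section 5.3.1.1 and Table 8, footnote i) schedules Phase 2 scans 6-weekly from C1D-2 to Week 30 and 9-weekly after that, each ±1 week. Treatment delays do not move the calendar. On the baseline scan, Table 8 footnote a says: "Tumor assessments must be performed within 21 Days of Cycle 1 Day -2". The Protocol's own PFS definition (8.1.2.1) has no missed-scan censoring, so this exclusion is a SAP addition.

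SAP 10.1 sets one data date: 14 September "2018 will be the cutoff date for all efficacy analyses". The only alternative PFS analysis, in SAP 10.8, is optional and serves "to consider the initiation of any anti-cancer post-treatment therapy as an event".

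**The concern.** The words require two missed assessments. The days attached to them fit one. The three tiers cover every possible date of the previous scan, so they are a complete algorithm, and they are the only operational form of the rule in the SAP. No inequality is stated, the ±1-week window is ignored, the origin of Day 168 and Day 210 is not given, and the start of the gap is undefined when there is no earlier post-baseline scan.

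Two competent programmers could therefore derive different event sets for the sole primary comparison (PFS, Arm A versus Arm C), which gates every secondary claim under SAP 10.2. The same rule feeds PFS for Arm B versus Arm C and DOR. The data date is fixed, so an event censored in error is not made up by a later one. No planned analysis relaxes this rule, so its effect would not be seen.

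**Working it through.** **Inputs.** Phase 2 scans at Weeks 6, 12, 18, 24, 30, 39, 48, … from C1D-2, each ±7 days (Protocol 5.3.1.1, Table 8). Limits of 84, 105 and 126 days with tier edges at Day 168 and Day 210 (SAP 10.3). Design: 85 events for A versus C, HR 0.63, one-sided α = 0.1 (SAP 4.3). C1D-2 is taken as Day 1, which matches the SAP's one-based labels (Week 24 Day 7 = Day 168).

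**1. The plan's figures.** (6+6)×7 = 84; (6+9)×7 = 105; (9+9)×7 = 126. Each is the interval from a scan to the next but one, so exactly one scan was missed. Two misses give nominally 18×7 = 126 (previous scan Week 6 or 12), 21×7 = 147 (Week 18), 24×7 = 168 (Week 24) and 27×7 = 189 (Week 30 on).

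**2. With the window.** Both scans can move 7 days, so each gap spans its nominal value ±14:

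| Previous scan | SAP limit, scan on its due date | One miss | Two misses |
|---|---|---|---|
| Weeks 6, 12 | 84 | 70–98 | 112–140 |
| Week 18 | 84 | 70–98 | 133–161 |
| Week 24 | 105 | 91–119 | 154–182 |
| Week 30 on | 126 | 112–140 | 175–203 |

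One-miss and two-miss ranges do not overlap for a given visit. The SAP limits lie in the middle of the one-miss ranges, so every two-miss progression is censored as intended, and some one-miss progressions are too.

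**3. Share of single-miss progressions censored.** Let u and v be the offsets of the previous and the progression scan, −7 to +7, giving 15×15 = 225 pairs. For Weeks 6, 12, 18 and 39 on, gap − limit = v − u.
- P(gap > limit) = 105/225 = 47%; P(gap ≥ limit) = 120/225 = 53%.
- If every scan is exactly on its due date: 0% with >, 100% with ≥.

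**4. Tier edge.** An on-time Week 24 scan is Day 169. One day early it is Day 168 and takes the 84-day limit. For Days 162–168 the one-miss gap to Week 39 is 99–119 days, always over 84. An early Week 30 scan (Days 204–210) takes 105 days against a one-miss gap of 120–140. These progressions are censored in every case. For Weeks 24 and 30 overall, the 7 early offsets contribute 7×15 = 105 pairs and the other 8 contribute 28 (>) or 36 (≥): 133/225 = 59% and 141/225 = 63%. If C1D-2 were Day 0, even on-time Week 24 and Week 30 scans would fall in the lower tier.

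**5. No earlier post-baseline scan.** Suppose only Week 6 is missed and progression is found at Week 12. Counted from a baseline scan x days before C1D-2 (x = 0–21), the gap is 84 + x + v, that is 77–112 days. It always exceeds 84 when x ≥ 8, and the subject would be censored at randomization. Counted from C1D-2, the Week 12 scan falls at 77–91 days and the Week 18 scan at 119–133.

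**6. Deaths.** After a last scan k days late (k = 0–7), the second nominal scan date comes limit − k days later. A gap over the limit therefore does mean that two due dates have passed. Only the window is ignored: for an on-time last scan, the second window closes 7 days after the limit.

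**7. Power.** Power = Φ(|ln 0.63|·√d/2 − 1.2816). At d = 85 this is 80.2%, which agrees with the SAP's claim of at least 80%. Assume a share s of the 85 events are single-miss progressions:
- s = 2%, half censored: 85×0.02×0.5 = 0.85 events lost, d = 84.15, power 79.9%.
- s = 15%, half censored: 6.4 lost, d = 78.6, power 77.8%.
- All censored: 1.7 to 12.8 lost, d = 83.3 to 72.25, power 79.6% to 75.2%.
- None censored: 80.2%.

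**The case against.** The day counts follow e.g., so the verbal rule governs and a careful programmer would count visits. There is also a coherent reading of the numbers: a gap longer than two scheduled intervals means that two due dates have gone by without a scan. With >, an exactly on-schedule single miss is not censored, and the 100% figure under ≥ contradicts the words themselves. The baseline case depends on counting from the screening scan, whereas censoring at randomization suggests counting from about C1D-2. The size of the effect on the primary test rests on assumed rates. The cutoff was predicted after 95 observed events, and if those were counted under the 10.3 rules, the date already allows for some loss.

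Much of this is fair. The problem is conditional on the counts being programmed, the numerical effect cannot be established from the documents, and they do not say how the 95 events were counted. But the due-date reading works for deaths and not for progression found at a scan. That scan may itself be the second assessment, done within its window, in which case only one was missed. The tier-edge result needs no assumption about the spread of scan dates. The SAP's reference to the previous scan leaves the baseline start open. Whatever the prediction allowed for, the cutoff is now a date and not an event count.

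**Conclusion.** The concern holds. The day counts in SAP 10.3 describe one missed assessment, and the rule is worded for two or more. If the counts are programmed, some single-miss progressions are censored under either inequality. With scan dates uniform within their windows the share is 47–53%, or 59–63% after a Week 24 or Week 30 scan, and it is 100% when that scan was early. If the baseline scan starts the gap, it is also 100% for a lone missed Week 6 when that scan was 8 or more days before C1D-2.

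The effect on the primary test is probably small. The Protocol keeps the scan calendar fixed, the rule is the same in all blinded arms, and no direction of bias is claimed. The power range of 79.9–77.8% depends on an assumed 2–15% share of single-miss progressions and on half being censored, since the documents give neither a missed-scan rate nor a distribution of scan dates. The reason to act is that the event set of the sole primary endpoint should not depend on a programmer's reading.

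**What to change.** Revise SAP 10.3 as follows.

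- Define the rule by counting missed scheduled visits, and set the tier by the scheduled visit of the previous scan instead of Day 168 and Day 210.
- For progression at a scheduled scan, censor only if the gap is >98 days (previous scan at Week 6, 12 or 18), >119 days (Week 24) or >140 days (Week 30 or later).
- With no earlier post-baseline scan, count from C1D-2 and censor only if both Week 6 and Week 12 were missed, that is, if the first post-baseline scan is >91 days after C1D-2.
- For deaths and off-schedule progressions, censor only if the windows of two consecutive scheduled assessments have closed without a scan. The day limits above hold only for in-window scheduled scans; otherwise the visit count decides.
- State the inequality and which day is Day 1.
- Add a sensitivity analysis of PFS, Arm A versus Arm C, that drops only the missed-assessment censoring and keeps the new-therapy censoring and the blind-break cutoff.

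The cost is SAP wording, a per-subject visit calendar in the PFS derivation and one more analysis. The trade-off is that slightly longer gaps are tolerated before censoring.

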## **10.4 Primary Efficacy Analysis**

### **10.4.1 Progression-Free Survival (Arm A versus Arm C)**

Time to PFS will be analyzed by Kaplan-Meier methodology and compared between Arm A and Arm C using a two-sided log-rank test stratified by LDH level. KM plots of these two treatment arms will be presented. Median PFS time and the corresponding 80% confidence interval will be calculated and constructed via Brookmeyer and Crowley (1982). A hazard ratio estimate of Arm A vs. Arm C and the corresponding 80% confidence interval will be obtained from a Cox proportional hazards model stratified by LDH level. In addition, progression free survival rates at Month 3 and 6 with their corresponding 80% CIs will also be provided using Kaplan-Meier estimation.

## **10.5 Secondary Efficacy Analyses**

### **10.5.1 Progression-Free Survival (Arm B versus Arm C)**

Time to PFS will be analyzed by Kaplan-Meier methodology and compared between Arm B and Arm C using a two-sided log-rank test stratified by LDH level. KM plots of these two treatment arms will be presented. Median PFS time and the corresponding 80% confidence interval will be calculated and constructed via Brookmeyer and Crowley (1982). A hazard ratio estimate of Arm B vs. C and the corresponding 80% confidence interval will be obtained from a Cox proportional hazards model stratified by LDH level.

### **10.5.2 Objective Response Rate (Arm A vs Arm C and Arm B vs Arm C)**

The objective response rate and corresponding 80% confidence interval will be estimated and compared between Arm A and Arm C as well as between Arm B and Arm C, respectively, using a two-sided Cochran-Mantel-Haenszel test stratified by LDH level. In addition, waterfall plots depicting best percentage of change in each subject's sum of target lesion sizes will be displayed by each treatment arm.

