## **4.0 Study Objectives**

The objectives of the Phase 1 dose escalation are:

Primary Objectives:

- To establish the Maximum Tolerated Dose (MTD) and to establish the Recommended Phase 2 Dose (RPTD) and schedule for veliparib in combination with carboplatin and etoposide.
- To evaluate the pharmacokinetic interaction between veliparib and etoposide.

Secondary Objective:

- To evaluate the safety of maintenance veliparib monotherapy at 400 mg BID in subjects completing 4 cycles of carboplatin, etoposide and veliparib without evidence of disease progression.

The objectives of Phase 2 are:

Primary Objective:

- To evaluate if veliparib in combination with carboplatin and etoposide followed by veliparib maintenance monotherapy results in improved progression free survival (PFS) versus placebo in combination with carboplatin and etoposide followed by placebo monotherapy in subjects with treatment-naïve ED SCLC.

Secondary Objectives:

- To evaluate if veliparib in combination with carboplatin and etoposide followed by placebo monotherapy results in improved progression free survival (PFS) versus placebo in combination with carboplatin and etoposide followed by placebo monotherapy in subjects with treatment-naïve ED SCLC.
- To evaluate if veliparib in combination with carboplatin and etoposide results in improved objective response rate (ORR) versus placebo in combination with carboplatin and etoposide, at the time of completion of combination therapy.
- To evaluate if veliparib in combination with carboplatin and etoposide followed by veliparib maintenance monotherapy results in improved overall survival (OS) versus placebo in combination with carboplatin and etoposide followed by placebo monotherapy.
- To evaluate if veliparib in combination with carboplatin and etoposide followed by placebo monotherapy results in improved overall survival (OS) versus placebo in combination with carboplatin and etoposide followed by placebo monotherapy.

- To further evaluate the safety of veliparib in combination with carboplatin and etoposide followed by veliparib maintenance monotherapy.

Tertiary Objectives are:

- To evaluate if veliparib in combination with carboplatin and etoposide followed by veliparib maintenance monotherapy results in improved duration of overall response (DOR) versus placebo in combination with carboplatin and etoposide followed by placebo monotherapy.

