### **Phase 2 Randomized Double-Blind**

The veliparib dose and schedule for the Phase 2 was determined to be 240 mg BID on a 14 day schedule based on the analysis of Phase 1 data.

Approximately 180 total subjects with treatment-naïve ED SCLC will be enrolled at the 240 mg BID veliparib/placebo dose and 14 day schedule in the Phase 2 double-blinded portion of the study. They will be randomized in a 1:1:1 ratio to one of three treatment arms:

Arm A: veliparib 240 mg in combination with carboplatin/etoposide followed by veliparib 400 mg BID monotherapy

Arm B: veliparib 240 mg in combination with carboplatin/etoposide followed by placebo monotherapy

Arm C: placebo in combination with carboplatin/etoposide followed by placebo monotherapy

Subjects in all Phase 2 study arms will receive a minimum of 4 cycles of combination therapy unless disease progression or unacceptable toxicity warrants earlier discontinuation from the treatment. Additional 2 cycles of combination therapy (e.g., up to a total of 6 cycles) may be administered at the investigators discretion if subject status at the completion of initial 4 cycles warrants continued combination treatment and/or if local SOC guidelines require 6 cycles of platinum-based therapy. In the combination cycles of Arms A and B, subjects will receive veliparib at 240 mg BID on a 14-day schedule, Arm C will receive matching placebo. After completion of the chemotherapy combination cycles (at least 4), subjects without evidence of disease progression will receive veliparib at 400 mg BID continuous dosing (21-day cycles) (Arms A), or

matching placebo (Arms B and C) as per treatment arm assignment, until disease progression or unacceptable toxicity occurs (Figure 2).

Subject randomization for Phase 2 will be stratified by baseline LDH level (> ULN versus ≤ ULN), and gender.

[figure not shown]

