#### **8.1.4.2 Objective Response Rate**

The objective response rate at the time of completion of combination therapy will be estimated and compared between Arm A + B combined and Arm C, using a Cochran-Mantel-Haenszel test stratified by LDH level. A two-sided, stratified CMH test

*P* value will be provided. In addition, a 95% confidence interval will be constructed for the estimated proportions.

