## **4.0 Study Objectives, Design and Procedures**

### **4.1 Objectives**

The primary objective of the study is to evaluate if the addition of veliparib in combination with carboplatin and etoposide followed by veliparib maintenance monotherapy results in improved progression free survival (PFS) versus placebo in combination with carboplatin and etoposide followed by placebo monotherapy in subjects with treatment-naïve ED SCLC.

The secondary objectives of the study are to evaluate (1) if veliparib in combination with carboplatin and etoposide followed by placebo monotherapy results in improved PFS versus placebo in combination with carboplatin and etoposide followed by placebo monotherapy in subjects with treatment-naïve ED SCLC; (2) if veliparib in combination with carboplatin and etoposide results in improved objective response rate (ORR) versus placebo in combination with carboplatin and etoposide, at the time of completion of maintenance therapy, or completion of combination therapy if subject was not involved in maintenance phase. In protocol v.5 dated 22 NOV 2016, Chapter 4.0, objective response rate is to be evaluated by the combination therapy for all subjects. We modified the analysis period by adding maintenance phase following ITT (intent-to-treat) population principle to avoid observation bias; (3) if veliparib in combination with carboplatin and etoposide followed by veliparib maintenance monotherapy results in improved overall survival (OS) versus placebo in combination with carboplatin and etoposide followed by placebo monotherapy; (4) if veliparib in combination with carboplatin and etoposide followed by placebo monotherapy results in improved OS versus placebo in combination with carboplatin and etoposide followed by placebo monotherapy; (5) to further evaluate the safety of veliparib in combination with carboplatin and etoposide followed by veliparib maintenance monotherapy.

The tertiary objectives are to (1) evaluate if veliparib in combination with carboplatin and etoposide followed by veliparib maintenance monotherapy results in improved duration of overall response (DOR) versus placebo in combination with carboplatin and etoposide

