### **4.3 Sample Size**

Assuming a median PFS of 5.5 months for placebo in combination with carboplatin and etoposide followed by placebo monotherapy (Arm C) and a hazard ratio of 0.63 for veliparib in combination with carboplatin and etoposide followed by veliparib monotherapy (Arm A) versus Arm C, a total of 85 PFS events will provide an least 80% power to detect a statistically significant difference between Arm A and Arm C at a one-sided  $\alpha = 0.1$ .

Further assuming a hazard ratio of 0.75 for veliparib in combination with carboplatin and etoposide followed by placebo monotherapy (Arm B) versus Arm C, a total of 126 PFS events will be observed across all three arms at the time when 85 PFS events are observed for Arm A and Arm C combined. A total of approximately 180 subjects (60 subjects per treatment arm) will be enrolled into the study to obtain the 126 PFS events.

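### The SAP replaces the Protocol's pooled A+B versus C response test with two separate tests running into maintenance, while keeping the combination-therapy objective and not explaining why pooling was dropped

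*SAP*

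**What the plan says.** Protocol 4.0 sets the ORR objective as "To evaluate if veliparib in combination with carboplatin and etoposide results in improved objective response rate (ORR) versus placebo in combination with carboplatin and etoposide", evaluated when combination therapy is complete. Protocol 8.1.4.2 matches it: ORR "at the time of completion of combination therapy will be estimated and compared between Arm A + B combined and Arm C", by a Cochran-Mantel-Haenszel (CMH) test stratified by LDH. The design supports pooling. Protocol 5.1 says "In the combination cycles of Arms A and B, subjects will receive veliparib at 240 mg BID on a 14-day schedule", so A and B differ only in maintenance.

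The SAP changes two things.

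- **Comparison.** SAP 10.5.2 has ORR "compared between Arm A and Arm C as well as between Arm B and Arm C, respectively". SAP Table 5 lists only these two ORR tests, fifth and sixth of six, with no pooled entry.
- **Period.** SAP 4.1 evaluates ORR "at the time of completion of maintenance therapy, or completion of combination therapy if subject was not involved in maintenance phase" and gives a reason: "We modified the analysis period by adding maintenance phase following ITT (intent-to-treat) population principle to avoid observation bias".

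SAP 4.1 leaves the treatment contrast in the objective as the Protocol has it. SAP 10.3 also adds a requirement that responses be confirmed at least 28 days later.

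**The concern.** The objective, the comparison and the window no longer fit together. For a question about adding veliparib to carboplatin and etoposide, every subject in A and B is informative and on the same regimen. Each SAP test leaves half of them out.

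The longer window lets maintenance treatment into A vs C. B vs C is free of maintenance veliparib but is ranked last, so it can be declared significant only after A vs C succeeds.

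The reason given covers the period only, and it does not support the change. Intent-to-treat, as SAP 5.1 itself defines it, settles who is analysed and in which arm; it does not set how long response is assessed. Entry to maintenance also depends on being free of progression, so the new window varies with an outcome after randomisation.

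At stake are power for a formally ranked secondary endpoint and the meaning of a positive result.

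**Working it through.** **1. The plan's own sizing.** The documents size the trial on PFS only. Schoenfeld's formula with hazard ratio 0.63, one-sided 0.10 and 80% power gives

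d = 4(1.2816 + 0.8416)² / (ln 0.63)² = 4 × 4.508 / 0.2135 = 84.5, so 85 events.

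This matches SAP 4.3. The 126 total also reproduces: with exponential PFS and assumed uniform accrual over 0 to 24 months, Arm B contributes 41.4 to 41.7 events when A and C together reach 85. There is no ORR sample size or power to reproduce.

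**2. Inputs for ORR.**
- Arm sizes: "A total of approximately 180 subjects (60 subjects per treatment arm) will be enrolled into the study" (SAP 4.3), so pooled 120 vs 60 and separate 60 vs 60.
- Level: one-sided 0.10, fixed sequence (SAP 10.2).
- Control ORR: 50% to 70% (Protocol 3.1).
- Effect: not given. Assumed +10, +15 or +20 points, equal in A and B. Equality follows from the identical combination regimen when response is judged over that phase.

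**3. Precision.** With a common variance per subject, the variance ratio of separate to pooled is

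(1/60 + 1/60) / (1/120 + 1/60) = 0.0333 / 0.0250 = 1.33,

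so the standard error is 1.155 times as large.

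**4. Power.** Unstratified two-proportion approximation to the CMH test:

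power = Φ[(Δ − 1.2816 × SE₀) / SE₁],

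where SE₀ uses the overall response rate and SE₁ the separate arm rates.

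Control 60%, +15 points:
- Pooled: overall rate 0.70; SE₀ = √(0.21 × 0.025) = 0.0725; SE₁ = √(0.24/60 + 0.1875/120) = 0.0746. Power = Φ(0.766) = 77.8%.
- Separate: overall rate 0.675; SE₀ = √(0.2194 × 0.0333) = 0.0855; SE₁ = √(0.24/60 + 0.1875/60) = 0.0844. Power = Φ(0.479) = 68.4%.

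Pooled versus each separate test over the whole range:

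| Control ORR | +10 points | +15 points | +20 points |
|---|---|---|---|
| 50% | 49.8% vs 42.8% | 74.3% vs 65.0% | 90.8% vs 83.5% |
| 60% | 52.4% vs 44.7% | 77.8% vs 68.4% | 93.5% vs 87.2% |
| 70% | 58.1% vs 49.3% | 84.6% vs 75.7% | 97.2% vs 93.4% |

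The loss is 3.8 to 9.4 points. A 200,000-replicate binomial simulation agrees at control 60%, +15 points (77.7% pooled, 69.3% separate). There, A vs C would need an effect of about 17 points to match the pooled test at 15.

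**5. Confirmation and the window.** Four 21-day cycles last 12 weeks, and Phase 2 scans are every 6 weeks. A four-cycle subject is therefore scanned at about weeks 6 and 12. A response first seen at week 12 cannot meet the 28-day rule until the next scheduled scan, at about week 18, after combination therapy has ended. Restoring the Protocol's cut-off without addressing this would drop such responses.

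**The case against.** The strongest defence is that the two changes are really one. Once maintenance scans count, A and B are no longer on the same treatment, so pooling loses its basis and separate tests follow. The period change is openly disclosed. The Protocol's own ORR endpoint definition (8.1.2.2) has no time limit, and its synopsis derives ORR from scans continuing to progression. Combination therapy lasts four to six cycles, partly at the investigator's discretion, so a cut-off there also varies by subject. Per-arm ORR mirrors the PFS and OS comparisons.

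Much of this stands as explanation. But the SAP does not make the argument, and it leaves in place the objective that the pooled test was built to answer.

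Four stronger readings are tempting, and the documents do not support them.

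- *The SAP no longer answers the combination question at all.* B and C both receive placebo maintenance, so B vs C still isolates combination-phase veliparib, less precisely and ranked last.
- *A claim needs both tests, with only about a 55% chance that both succeed at control 60%, +15 points.* The fixed sequence lets A vs C be declared on its own.
- *Pooling is always the more powerful choice.* If maintenance veliparib raised response in A, A vs C could do better: with +20 in A and +10 in B at control 60%, 87.2% against 77.8% pooled. That would answer a different question.
- *The change was driven by results.* The SAP is dated 15 November 2018, after the 14 September 2018 cutoff, but SAP 12.0 describes unblinding as still to come.

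**Conclusion.** The mismatch is real: the ranked ORR tests in the SAP differ from Protocol 8.1.4.2 in comparison and in period, while the stated objective keeps the same treatment contrast. One change carries a reason that does not support it; the other carries none.

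The size is moderate: about 4 to 9 points of power for each separate test against the pooled one. This rests on assumed effects of 10 to 20 points, equal in A and B, control ORR of 50% to 70%, full enrolment of 60 per arm, and an unstratified approximation. The ORR tests come last in the hierarchy, so formal power matters only if all earlier tests succeed. The loss of a clear match between question and analysis applies regardless, because ORR will be reported and interpreted either way. The change should be made, but the primary analysis is unaffected.

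**What to change.** Before unblinding, amend SAP 10.5.2 and Table 5 so that a single ranked ORR test, A+B combined versus C by CMH stratified by LDH, replaces the two current entries. Count responses first documented by completion of combination therapy, and state that the confirming scan required in SAP 10.3 may fall after that point. Align the period in SAP 4.1. Report A vs C and B vs C over the whole treatment period as supportive estimates with confidence intervals.

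The cost is SAP wording and one derived response variable; no new data are needed. The downside is that there is no separate formal ORR claim per arm, and responses first seen in maintenance do not count in the ranked test.
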